8 ADVERSE EVENTS (AE/SAE)

8.1 Adverse Events

8.1.1 Definition AE

An Adverse Event is any untoward medical occurrence in a patient or clinical investigation subject administered a pharmaceutical product and which does not necessarily have to have a causal relationship with this treatment.

An Adverse Event (AE) can therefore be any unfavourable and unintended sign (including an abnormal laboratory finding, for example), symptom, or disease temporally associated with the use of a medicinal product and/or laser treatment, whether or not considered related to the medicinal product. (ICH Guideline E2A).

8.1.2 Adverse Drug Reaction (ADR)

An adverse drug reaction of a medicinal product **carrying a marketing authorization** is defined in Article 2(n) of Directive 2001/20/EC as all “untoward and unintended responses to an investigational medicinal product which occurs at doses normally used”.

8.1.3 Documentation and Reporting

Adverse events will be documented on special AE-forms electronically in eCRF from first Ranibizumab administration until 4 weeks after the last trial-related intervention.

At each visit, the patient will be asked a non-leading question such as “Have you had any health problems since the last visit”. In this study **ONLY** AEs related to the study procedures and AEs related study drug and critical ocular events will be recorded. In case of endophthalmitis, it will be documented on the AE-form which kind of ranibizumab preparation was used (pre-filled syringe or syringe prepared at the pharmacy or syringe prepared intraoperatively).

If an AE fulfils any of the criteria for an SAE (see chapter 8.4.1 for SAE-definition), both the AE pages of the eCRF **and** the paper based SAE form must be completed. This also applies **ONLY** to events **considered to be related to trial treatment**.

For both serious+related and non-serious+related AEs, documentation should be supported by an entry in the patient's health record. Required information in the patient's health record should include:

- type of AE
- grade/severity/intensity acc. to e.g. CTCAE
- seriousness (see also section 18.1)
- onset date
- end date
- actions required
- outcome
- **assessment of its relationship to trial treatment**

Adverse Events are classified by their seriousness, intensity/severity and relationship to the trial treatment (see also 18.1)

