4.2 Exclusion Criteria

Patients will be excluded for ANY ONE of the following reasons:

1. CRVO with ischemic maculopathy defined as diameter of the foveolar avascular zone larger than 2 optic disc diameters
2. Macular edema due to another etiology than retinal vein occlusion (e.g. diabetic maculopathy, uveitis, age related macular degeneration, Irvine-Gass syndrome)
3. History of idiopathic central serous chorioretinopathy
4. Presence of vitreoretinal interface disease (e.g. vitreomacular traction, epiretinal membrane), either on clinical examination or in OCT
5. An eye that, in the investigator's opinion, would not benefit from resolution of macular edema, such as eyes with foveal atrophy, dense pigmentary changes, or dense subfoveal hard exudates
6. Aphakia in the study eye
7. Scatter laser photocoagulation or macular photocoagulation in the study eye prior to study entry
8. Intraocular or periocular injection of steroids in the study eye prior to study entry
9. Previous use of an anti-VEGF drug in the study eye
10. Cataract surgery or any other intraocular surgery in the study eye within 3 months prior to study entry
11. Uncontrolled glaucoma (defined as intraocular pressure ≥ 30 mm Hg despite treatment with maximal anti-glaucoma medications)
12. History of stroke, myocardial infarction, transient ischemic attacks within 3 months prior to the study
13. Pregnancy (positive urine pregnancy test) or lactation

14. The presence of active malignancy, including lymphoproliferative disorders.
15. History of allergy to fluorescein or any component of the ranibizumab formulation
16. Active intraocular infection
17. Participation in another simultaneous interventional medical investigation or trial
18. Women with child bearing potency without effective contraception (i. e. implants, injectables, combined oral contraceptives, some IUDs or vasectomised partner) during the conduct of the trial.

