8.1.4 AEs related to the trial treatment

AEs related to the trial treatment are:

- adverse drug reactions of the study drug
- adverse events due to the injection of the study drug
- adverse device effects of photocoagulation

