8.1.5 Critical ocular events

Critical ocular events will be documented on the AE eCRF during the complete study participation.

Following events are defined as critical ocular event:

- Any intraocular inflammatory response regardless of suspected etiology.
- Any case of new onset of a clinically significant increase in IOP, at any time, that required treatment.
- Any abrupt, clinically significant decrease in BCVA ≥ 15 letters
- Any new onset of retinal vein occlusion (central or branch) with new macular edema (ME) requiring the treatment with intravitreal drugs. The CRVO or BRVO will be defined as a new event if the macular edema occurs later than 2 months after the last intravitreal injection AND new intraretinal bleedings or microaneurysms will be detected and/or new venous dilatation will be detected when compared with visit prior to new detection of ME.
- An event that may - in the opinion of the investigator - require medical intervention to prevent permanent loss of sight.

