8.4 Serious Adverse Events

8.4.1 Definition SAE

A Serious Adverse Event (experience) or reaction is (according to ICH-Guideline E2A) any untoward medical occurrence that at any dose:

- **results in death,**
- **is life-threatening,**

Note: The term “life-threatening” in the definition of “serious” refers to an event in which the patient was at risk of death at the time of the event; it does not refer to an event which hypothetically might have caused death had it been more severe.

- **requires in-patient hospitalisation or prolongation of existing hospitalisation¹,**
- **results in persistent or significant disability/incapacity or**
- **is a congenital abnormal/birth defect**

Medical and scientific judgement should be exercised in deciding whether expedited reporting is appropriate in other situations, such as important medical events that may not be immediately life-threatening or result in death or hospitalisation but may jeopardise the patient or may require intervention to prevent one of the other outcomes listed in the definition above. These should also usually be considered serious.

In the CoRaLa-II study **ONLY** adverse events related to the study procedures will be recorded as SAE if they fulfil any SAE-criteria (SAR).

Additionally, any untoward medical occurrence that caused or threatened significant loss of visual acuity defined as ≥ 30 ETDRS letters will be considered as SAE.

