8.4.2 Documentation and Reporting Obligations: INVESTIGATOR

Serious Adverse Events have to be documented on the SAE-forms and the investigator must report them to the sponsor immediately. If more information about the SAE becomes available later, it must also be reported to the sponsor immediately.

SAE reporting will be performed from first injection of the study drug (Visit 1) up to 4 weeks after the last trial-related intervention, which is (at latest) Visit 24.

In the event of a patient’s death, the investigator/deputy or the authorised medical staff provides the leading ethics committee(s), all involved ethics committees in multi-centred trials, the responsible federal authorities and the sponsor with all further information needed to fulfil their tasks **upon request**.

In all the reports, personal data are to be pseudonymized by using the patient’s identification code. It must be possible to relate the initial and all follow-up reports to each other by means of the patient identification number.

1 In general, hospitalisation means that the patient stays (usually at least an overnight stay) at the hospital or emergency ward for observation and/or treatment. Complications that occur during the stay are AEs. If a complication prolongs hospitalisation or fulfills any other serious criteria, the event is serious.

Hospitalisation for elective treatment of a pre-existing condition that did not worsen from baseline is not considered an AE.

The investigator, the deputy or the authorised medical staff must report every Serious Adverse Event as soon as getting knowledge of it to the following address:

ZKS Leipzig/Pharmacovigilance
 Universität Leipzig
 Zentrum für Klinische Studien Leipzig
 [name]
 [contact]
E-mail: [contact]

[contact]

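### Adverse event recording opens only at the first ranibizumab injection, so in-scope reactions to screening procedures, notably the required fluorescein angiography, fall outside the window

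*Protocol*

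**What the plan says.** Two statements fix the start of recording. Protocol section 8.1.3 documents AEs in the eCRF "from first Ranibizumab administration until 4 weeks after the last trial-related intervention". Section 8.4.2 agrees for serious events: "SAE reporting will be performed from first injection of the study drug (Visit 1").

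Two statements fix the scope. Section 8.1.3 restricts the AE record to certain classes: "AEs related to the study procedures and AEs related study drug and critical ocular events will be recorded". Section 8.4.1 does the same for serious events: "adverse events related to the study procedures will be recorded as SAE if they fulfil any SAE-criteria". Both name the study procedures and neither limits the term to procedures after the first injection.

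Section 8.1.5 sets a separate window for one class: "Critical ocular events will be documented on the AE eCRF during the complete study participation".

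A narrower term also appears. Section 8.1.3 limits the SAE form to events "considered to be related to trial treatment", and section 8.1.4 lists what that covers: reactions to the drug, events due to its injection, and "adverse device effects of photocoagulation". Angiography is not in that list.

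**The concern.** The stated scope and the stated start do not fit together. Study procedures begin at the screening visit, after consent and before the first injection. The one that matters most for safety is the fluorescein angiography. It is needed to show the non-perfusion required by inclusion criterion 6, it is done under the trial's imaging protocol, and it is read centrally. The protocol treats fluorescein as a possible hazard, since exclusion criterion 15 reads "History of allergy to fluorescein or any component of the ranibizumab formulation". That criterion removes only patients with a known allergy. A first reaction can still occur at screening.

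At stake is safety capture. As written, a serious reaction to the screening angiography has no defined route into the SAE database of section 8.4.3, and so none into reports that draw on it. A patient who reacts and then fails screening never reaches the visit at which recording opens. Sites also receive conflicting instructions on critical ocular events before Visit 1.

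**Working it through.** The protocol gives no figure to reproduce here. The check is a comparison of sections, followed by simple counts.

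1. **Scope.** Sections 8.1.3 and 8.4.1 include (S)AEs related to the study procedures.
2. **Window.** Sections 8.1.3 and 8.4.2 open it at the first injection. Section 6.3.2 places that at baseline, Visit 1 (Day 1).
3. **What comes before the window.** Section 6.1 requires consent before any trial-specific procedure. Section 6.3.1 then lists, at screening, intraocular pressure, gonioscopy, OCT, OCT-angiography, fundus photography and fluorescein angiography. Section 6.2 places randomisation between Day -14 and Day 0.
4. **Scope and window combined.** A reaction to a procedure in step 3 satisfies step 1 and fails step 2. This is so even when screening and Visit 1 share a day, because the angiography still precedes the injection.
5. **Critical ocular events.** Section 8.1.5 covers all of participation. Section 6.3.1 has no item for adverse or critical ocular events; the first is in section 6.3.2. The schedule row for these events likewise starts at Visit 1. The text and the schedule therefore agree with each other and differ from 8.1.5.
6. **Terms.** Under *study procedures* (8.1.3, 8.4.1) an angiography reaction counts. Under *trial treatment* (8.1.3 for the SAE form, 8.1.4) it does not appear to. The ambiguity applies to later angiographies as well.

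**Size, from the protocol's own numbers:**

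- Length of the gap for one screening visit: from Day -14 to Day 0 is 0 - (-14) = 14 days, with Visit 1 on Day 1, so about 14 days at most. Section 6.3.1 allows screening and baseline on the same day, so the minimum is the time from angiography to injection, under one day.
- Patients: section 3.3 plans 130 assessed and 110 allocated, so 130 - 110 = 20 not allocated. Both 130 and 20 are upper planning figures for this purpose. Angiography comes last in the list in 6.3.1, and a patient who fails on an earlier assessment need not have it.
- Angiographies: sections 6.3.1 to 6.3.5 name screening, Visit 3, Visit 9, Visit 16 and Visit 24, which makes five. One precedes the window: 1/5.
- Events lost: the protocol gives no reaction rate, so no count can be stated.

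**Effect on the analyses:** no trial drug or laser is given before Visit 1. The full analysis set, from which the safety set is drawn, requires at least one study intervention (section 9.5.1). The primary endpoint does not use AE data.

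**The case against.** The best defence is that scope and window apply jointly: 8.1.3 says when events are recorded and then which ones. The AE definition in 8.1.1 refers to a subject given a pharmaceutical product and to the use of a medicinal product or laser, so a start at the first dose follows naturally. *Study procedures* is never defined and might mean only the interventions listed in 8.1.4. In addition, AE documentation takes place at Visit 1, where the patient is asked about problems since the previous visit, and source records exist in any case (section 11.2).

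Part of this stands. The undefined term is a real source of the problem, and a screening reaction would probably be noted somewhere in the source file. But 8.1.1 speaks of a pharmaceutical product in general and cannot cancel the explicit mention of study procedures in 8.1.3 and 8.4.1. The question at Visit 1 may bring up a reaction that the written window then excludes, and it never reaches a patient who fails screening.

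A reader might also infer that all events between randomisation and Visit 1 are lost. The protocol does not support that. Unrelated AEs that are not critical ocular events are left out throughout the trial by design, so the start date does not cause their loss. Critical ocular events already have a wider stated window in 8.1.5, although the visit text and schedule do not carry it out. Nor does the protocol show that a reacting screen failure would leave no record at all; what is missing is a place in the trial's AE and SAE data.

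**Conclusion.** The point holds as a limited inconsistency in safety capture. Procedure-related (S)AEs at screening are in scope under 8.1.3 and 8.4.1 but outside the window under 8.1.3 and 8.4.2, and critical ocular events before Visit 1 are promised in 8.1.5 without any entry to record them. The gap lasts from under one day to about 14 days per screening visit and touches at most about 130 assessed patients, of whom at most about 20 would never come under the window.

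This rests on reading *study procedures* to include the protocol-required screening angiography, which is the plain sense of the term given sections 4.1, 6.1 and 6.3.1. The sample size, the primary analysis and the comparison between arms are not affected. The point merits correction because in-scope safety events are dropped by the rule as written and the remedy is cheap.

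**What to change.** - In sections 8.1.3 and 8.4.2 and in the schedule, start the recording of procedure-related (S)AEs and of critical ocular events at signed informed consent. Add the matching item to section 6.3.1.
- Keep Visit 1 as the start for drug- and laser-related events.
- List events before Visit 1 separately, including those in screen failures, so that the comparison between arms stays as planned.
- In the same edit, reconcile *trial treatment* (8.1.3, 8.1.4) with *study procedures* (8.1.3, 8.4.1), so that it is clear that angiography reactions count at all visits.

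The cost is protocol wording, an AE form available from screening in the eCRF, and a few more entries. No visit or procedure is added.

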8.1.4 AEs related to the trial treatment

AEs related to the trial treatment are:

- adverse drug reactions of the study drug
- adverse events due to the injection of the study drug
- adverse device effects of photocoagulation

8.1.5 Critical ocular events

Critical ocular events will be documented on the AE eCRF during the complete study participation.

Following events are defined as critical ocular event:

- Any intraocular inflammatory response regardless of suspected etiology.
- Any case of new onset of a clinically significant increase in IOP, at any time, that required treatment.
- Any abrupt, clinically significant decrease in BCVA ≥ 15 letters
- Any new onset of retinal vein occlusion (central or branch) with new macular edema (ME) requiring the treatment with intravitreal drugs. The CRVO or BRVO will be defined as a new event if the macular edema occurs later than 2 months after the last intravitreal injection AND new intraretinal bleedings or microaneurysms will be detected and/or new venous dilatation will be detected when compared with visit prior to new detection of ME.
- An event that may - in the opinion of the investigator - require medical intervention to prevent permanent loss of sight.

8.2 Further safety-relevant issues

During the course of the trial, every patient will be monitored closely to identify the

- Presence of rubeosis iridis or neovascularization in iridocorneal angle
- Presence of neovascularization of optic disk (NVDs) or retinal neovascularizations elsewhere (NVEs) at every visit if present.

8.3 Concomitant Diseases

Concomitant diseases will be recorded at *baseline* (Day 1). Changes will be assessed at the regular trial visits and recorded if present. Any worsening of concomitant diseases will be regarded as adverse event, but will only be documented in the eCRF, if related to the trial treatment.

8.4 Serious Adverse Events

8.4.1 Definition SAE

A Serious Adverse Event (experience) or reaction is (according to ICH-Guideline E2A) any untoward medical occurrence that at any dose:

- **results in death,**
- **is life-threatening,**

Note: The term “life-threatening” in the definition of “serious” refers to an event in which the patient was at risk of death at the time of the event; it does not refer to an event which hypothetically might have caused death had it been more severe.

- **requires in-patient hospitalisation or prolongation of existing hospitalisation¹,**
- **results in persistent or significant disability/incapacity or**
- **is a congenital abnormal/birth defect**

Medical and scientific judgement should be exercised in deciding whether expedited reporting is appropriate in other situations, such as important medical events that may not be immediately life-threatening or result in death or hospitalisation but may jeopardise the patient or may require intervention to prevent one of the other outcomes listed in the definition above. These should also usually be considered serious.

In the CoRaLa-II study **ONLY** adverse events related to the study procedures will be recorded as SAE if they fulfil any SAE-criteria (SAR).

Additionally, any untoward medical occurrence that caused or threatened significant loss of visual acuity defined as ≥ 30 ETDRS letters will be considered as SAE.

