3.5.2 Termination of the Whole Trial or of Individual Arms of the Trial

The trial can be terminated prematurely by the coordinating investigator in the event of

- marked increase of clinical events in the experimental arm
- changes in the risk-benefit considerations, e.g. as a result of unexpected adverse events
- new insights from other trials
- an insufficient recruitment rate.

The final decision regarding the premature termination of the trial will be made by the coordinating investigator based on recommendations of the DSMB and the biometrician.

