18.1.5 Outcome of an Adverse Event

The outcome of an Adverse Event is classified as follows:

- recovered/resolved
- recovering/resolving
- not recovered/not resolved
- recovered/resolved with sequelae
- fatal*
- unknown

*Note: A patient's death is not in itself an event, but the consequence of one. The event that led to the patient's death must be documented completely and reported even if death occurs four weeks after stopping medication and independent of whether or not there is a relation to the therapy or not.

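### Sections 8.1.3 and 8.4.1 limit SAEs to related events (ocular exceptions apart), while Section 18.1.5 requires every death to be reported whatever its cause; one death rule is needed

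*Protocol*

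**What the plan says.** Section 8.1.3 states that only "AEs related to the study procedures and AEs related study drug and critical ocular events will be recorded", and confines the paper SAE form to events "considered to be related to trial treatment". Section 8.4.1 first gives the usual seriousness list, including an event that "results in death", and then narrows it: only "adverse events related to the study procedures will be recorded as SAE if they fulfil any SAE-criteria".

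Two groups of events escape the relatedness condition. Under Section 8.1.5, "Critical ocular events will be documented on the AE eCRF during the complete study participation". Section 8.4.1 also counts as an SAE "any untoward medical occurrence that caused or threatened significant loss of visual acuity defined as" at least 30 ETDRS letters.

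Section 8.4.2 runs SAE reporting from the first injection to four weeks after the final trial intervention, at the latest Visit 24. For a death it adds only that further information goes to committees, authorities and sponsor when they ask for it.

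The note to Section 18.1.5 treats death as the outcome of an event. It requires that event to be fully documented and "reported even if death occurs four weeks after stopping medication and independent of whether or not there is a relation to the therapy".

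On analysis, Section 2.2 and the planned methods in Section 9.5.2 speak of (S)AEs together with (S)ARs. Section 9.2.4 names only (S)ARs and critical ocular events.

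**The concern.** A site that judges a death unrelated cannot follow both the main safety sections and the appendix. The recorded number of deaths then depends partly on which section the site read. Death is the one serious outcome for which a complete count in both arms should be beyond argument.

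For other non-ocular serious events, such as a stroke or myocardial infarction, entry into the record depends on a causality judgement made by staff who can know the arm. A reader of Sections 2.2 and 9.5.2 would expect the arms to be compared on all (S)AEs, but unrelated non-ocular ones are not collected.

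**Working it through.** There is no stated figure to reproduce, so the rules are set side by side.

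| Protocol section | Covers | Must be judged related? | Period |
|---|---|---|---|
| 8.1.3 | AE pages, SAE form | Yes, except critical ocular events on the AE pages | To four weeks after the final intervention |
| 8.4.1, 8.4.2 | SAEs | Yes, except losses of at least 30 letters | Same, at the latest Visit 24 |
| 8.1.5 | Critical ocular events | No | Whole participation |
| 18.1.5 | Event leading to death | No | Includes death four weeks after stopping; no end stated |

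**1. A test case.** Take a fatal non-ocular event during treatment that the site judges unrelated. Under 8.1.3 and 8.4.1 it is not recorded. Under 18.1.5 it is documented and reported. If an arm has k such deaths, the recorded number can lie anywhere from 0 to k, depending on how the sites read the protocol.

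**2. Timing.** Under 8.4.2 the window closes about one month after the final intervention, while observation runs to month 29. Section 1.2.1 cites treatment ending after 11 months in the predecessor study. A patient whose last intervention is at month 11 leaves the window at about month 12, so 29 − 12 = 17 months of observation lie outside it. A patient treated to month 23 leaves it at month 24, so 29 − 24 = 5 months lie outside. The window thus depends on when treatment ends, which is what the trial compares. Section 18.1.5 does not say whether it covers the later months.

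**3. Who applies the filter.** Section 18.1.3 gives the causality judgement to site staff. Section 6.2 puts the allocation in the medical record. Only the BCVA assessor is stated to be blinded, and no sham laser is described. Section 8.1.4 lists photocoagulation effects as a class of related event, and only the experimental arm receives study laser. The second opinion in Section 8.4.3 is formed on SAEs already received, so it cannot recover events that were never reported.

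**4. What the filter could do to non-ocular events (illustration only).** The event rates and attribution shares below are assumptions; the documents give none. Recorded rate = true rate × share judged related. The test is a two-sided exact Fisher test at 5%, with 110/2 = 55 patients per arm.

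| True rate, laser / control | Share judged related, laser / control | Recorded rate, laser / control | Probability of p ≤ 0.05 |
|---|---|---|---|
| 30% / 30% | 100% / 100% | 30% / 30% | 3.1% |
| 30% / 30% | 50% / 50% | 15% / 15% | 2.5% |
| 30% / 30% | 60% / 30% | 18% / 9% | 18.9% |
| 40% / 15% | 100% / 100% | 40% / 15% | 79.8% |
| 40% / 15% | 50% / 50% | 20% / 7.5% | 37.0% |
| 40% / 15% | 30% / 60% | 12% / 9% | 3.7% |

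Equal shares create no false difference but cost power. Unequal shares can create a difference or hide one.

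**5. Analysis wording.** Section 9.2.4 matches what is collected. Sections 2.2 and 9.5.2 name (S)AEs, of which the unrelated non-ocular ones are absent by design.

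**The case against.** The strongest reply is that related-only collection is deliberate. It recurs in the schedule footnotes and in Sections 8.1.3, 8.3 and 8.4.1, for a marketed drug used within its label and an established laser technique. Section 9.2.4 openly compares reactions and critical ocular events. The relatedness category in Section 18.1.3 is wide: events that concurrent disease could also explain, and events that cannot be judged, count as a reasonable possibility. Section 18.1.5 could also be read as a specific rule that overrides the general one. All of this stands as a defence of the design, and it rules out calling the restriction itself an error. It does not settle the conflict on deaths. The main sections state their own exceptions, deaths are not among them, and nothing presents the appendix note as a further one.

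Three stronger readings are tempting and are not supported:

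- **That only related events are recorded.** Critical ocular events and losses of at least 30 letters carry no relatedness condition, and neovascularization is assessed in every patient. Much of the ocular safety record is therefore unfiltered.
- **That the stopping criterion rests on the filtered record.** Section 3.5.2 refers to a "marked increase of clinical events in the experimental arm" without defining those events or naming the SAE record.
- **That the data board cannot see deaths.** Deaths without earlier success must be known for censoring under Section 9.2.1. Section 9.6 has central monitoring review drop-outs by reason, and Section 13.6 has the board evaluate all safety data. By-arm tables of deaths are not promised, but that does not amount to the board being unable to see them.

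**Conclusion.** The conflict is real and limited. Sections 8.1.3, 8.4.1 and 8.4.2 cannot be followed together with Section 18.1.5 for a death judged unrelated, and the period in which such a death counts is not fixed. For non-ocular events the record also depends on causality judged where allocation is known, and Sections 2.2 and 9.5.2 describe a broader comparison than the collected data allow.

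No size can be derived from the documents. The number of affected deaths is probably small: Section 9.4 reports two deaths per arm among the 22 patients of the predecessor study, all after more than four years, against 29 months here. The percentages in the illustration rest entirely on assumed rates and shares, and show direction only. That site staff know the arm when judging causality is an inference, though a well-supported one. Collecting every SAE regardless of cause would remove the filter altogether, but it is an option for the sponsor and not the correction of an error.

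**What to change.** - Reconcile Sections 8.1.3, 8.4.1 and 8.4.2 with Section 18.1.5: record and report every death in both arms irrespective of relation, with relatedness kept as an attribute. State the period in which the rule applies, the same for both arms and not dependent on when treatment ended.
- Tabulate deaths by arm for the data board and in the final safety analysis.
- Align Sections 2.2 and 9.5.2 with Section 9.2.4, and describe the arm comparison in all three as related (S)ARs, critical ocular events and all deaths.
- Optionally, record all SAEs irrespective of relation. The restriction of non-serious AEs can stay as it is.

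The cost is a wording amendment, a note to sites and a few additional forms. The primary endpoint, the sample size and the visit schedule are unaffected.
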